men will be screened for eligibility and will undergo the informed consent process. Once informed consent is signed, a physical examination will be performed, rapid HIV testing, phlebotomy for screening labs, and randomization will occur. During study visit 2 (time 1-6 weeks after study visit 1), men will be dispensed and instructed to take either Truvada® or Genvoya® for 10 days. After 3 to 5 consecutive days of dosing, participants will return for visit 3 where a urethral and penile swabs specimen, blood work, and a urine specimens will be obtained. During study visit 4 (time 10 days of consecutive drug dosing), men will return for repeat phlebotomy, urethral and penile swabs, collection of urine and rectal secretions, and rectal biopsy. After collection, biologic specimens will be immediately transported by courier to CDC (laboratory of [name]) for processing. Specimens will be processed immediately for ex vivo laboratory assays that will include Truvada® and/or Genvoya® drug concentrations, inflammatory cytokine levels, HIV target cell measurement and characterization by flow cytometry, and in vitro HIV infection assays. Comparison of assay results between the 2 study arms will help in determining the ability of the new formulated anti-HIV drug to penetrate different body compartments at the site of possible HIV exposure.

Participants may participate in more than one phase; however, at least 8 weeks must lapse after completion of 1 study phase before entry into another. Men who participate in more than one phase will not be consented again and do not have to repeat the screening visit (visit 1) when starting another phase; they will begin the new phase at visit 2.

Duration: The duration of this study is 3 years. Participants will be considered 'on-study' for no more than 12 weeks.

Sample size: For this protocol we will recruit 90 HIV-negative MSM or transgender women who are not taking hormone therapy who meet eligibility criteria outlined in the protocol.

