# PROJECT DESCRIPTION

**Public Health Relevance:** Information about new anti-HIV agents and how they penetrate through mucosal tissues will better inform scientists about the potential of new agents to be used for pre-exposure prophylaxis (PrEP).

**Goal**: To compare the body compartment pharmacokinetics and mucosal inflammatory effects of Truvada® vs. Genvoya®.

Version 6 04/21/17

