# Phase II

40 participants (20 in each study arm) will be enrolled in study phase 2.

Study visit 2 will occur 1-6 weeks after the screening visit. During visit 2, the study group assignment will be reviewed and participants will be provided with a single dose of Truvada® or Genvoya®. Drug will be dispensed through the Emory Investigational Drug Service. Depending on the study arm they were assigned to, MSM will be dispensed 1 day of Truvada® or Genvoya® and instructed on dosing for that day. Four to six hours after the drug is taken, a urine sample, 4 tablespoons of blood will be drawn from the participants arm, as well as, penile and urethral swabs will be collected from participants. These sample will be used at CDC to develop an assay to detect Truvada® and Genvoya® in the body. All specimens will be coded with a unique numeric identifier such that the CDC laboratories that receive the specimens will be unable to link them back to the study participants. Participants will be requested to abstain from receptive anal intercourse 3 days prior to study visit 2 and while taking study product.

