# Risks of Truvada® for PrEP

Truvada® is a combination pill that contains the medications tenofovir and emtricitabine. In clinical trials of PrEP for MSM, the drug was well tolerated. Nausea was more common among participants taking the medication than among those taking placebo (9% vs. 5%). There were no differences in severe or life-threatening adverse laboratory events between the active and placebo group. Adverse events associated with tenofovir can include a transient decrease in renal function and slight decreases in bone mineral density. Both of these effects occur with prolonged use of the medication and are not expected to occur with the limited 7-day dosing in this protocol. Nausea was more common among participants taking the medication than among those taking placebo (9% vs. 5%). There were no differences in severe or life-threatening adverse laboratory events between the active and placebo group. Adverse events associated with tenofovir can include a transient decrease in renal function and slight decreases in bone more common among participants taking the medication than among those taking placebo (9% vs. 5%). There were no differences in severe or life-threatening adverse laboratory events between the active and placebo group. Adverse events associated with tenofovir can include a transient decrease in renal function and slight decreases in bone mineral density. Both of these effects occur with prolonged use of the medication and are not expected to occur with the limited 7-day dosing in this protocol.

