### Risk of Genvoya®

Genvoya® is a combination anti-HIV medication that contains the drugs tenofovir alafenamide, emtricitabine, elvitegravir, and cobicistat. Based on clinical trials previously conducted of Genvoya®, the drug showed to be well tolerated. According to participants, the most common side effect shown was nausea with diarrhea being the second most common side effect. Of those who reported this adverse event, 0.9% and 1.5 % discontinued treatment regardless of the severity. Adverse events associated with Genvoya® can include a transient decrease in renal function and slight decreases in bone mineral density. There is also a possibility of lactic acidosis, which can be hard to identify during early stages. These effects occur with prolonged use of the medication and are not expected to occur with the limited 10-day dosing in this protocol. In contrast to Truvada®, there have been no clinical trials of Genvoya® for HIV pre-exposure prophylaxis. However, similar concerns with acquisition of HIV infection and development of HIV drug resistance as discussed above also apply to Genvoya®.

Genvoya® can also cause flare-ups in those who have hepatitis B virus. It can cause the Hepatitis B virus to suddenly return in a worse form than before if treatment was provided. For this reason, it is important that participants not participate in the study if they are known to have Hepatitis B. Nonetheless, the maximum 10 day dosing regimen for this study is unlikely to cause flare-ups in Hepatitis B even if not diagnosed.

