Unique Protocol ID: IRB00092488

NCT02985996

Statistical Analysis Plan

Truvada® vs. Genvoya®

Principal Investigator [name] [name]

01/15/2019

Demographic, behavioral, clinical, and laboratory data will be collected from the screening clinical assessment, the study entry physical examination and screening laboratory tests, and rectal biopsy visits.

Median (range) drug levels will be calculated at baseline and each of the protocol specified follow-up time points. Differences in median drug levels between baseline and study visit follow-up visits will be analyzed with non-parametric Wilcoxon-signed rank tests. A p-value of <0.05 will be considered significant.

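### The SAP has one unadjusted 0.05 rule, names no primary comparison and no multiplicity control, and leaves open which between-arm contrast answers the protocol's goal

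*SAP*

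**What the plan says.** The SAP's inferential content is two sentences. The first sets the test: "Differences in median drug levels between baseline and study visit follow-up visits will be analyzed with non-parametric Wilcoxon-signed rank tests". The second sets the threshold: "A p-value of <0.05 will be considered significant". It does not say whether tests are one- or two-sided. It names no primary analyte, compartment or time point, and no adjustment for multiple tests. It contains no test between arms and does not mention inflammatory markers.

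The protocol aims at something different. The Goal under Project Description is "To compare the body compartment pharmacokinetics and mucosal inflammatory effects of" the two products. The Abstract lists, besides drug concentrations, "inflammatory cytokine levels, HIV target cell measurement and characterization by flow cytometry, and in vitro HIV infection assays", and then states: "Comparison of assay results between the 2 study arms will help in determining the ability" of the newer product to reach sites of possible exposure. The protocol attaches no test, threshold or ranking to any of these results.

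**The concern.** A two-arm trial with many samples per participant produces many candidate results. If no contrast is singled out beforehand and the only rule on the page is an unadjusted 0.05, any isolated p-value below that level can later be presented as the finding. A reader could not tell a planned answer from a selected one.

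The risk is not equal across comparisons. When on-drug levels are compared with pre-drug levels, nearly every null hypothesis is false, so few significant results would be spurious. The exposure lies in the between-arm drug contrasts and the inflammatory contrasts, where no difference is plausible. Those are the comparisons the protocol promises and the SAP leaves unspecified.

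**Working it through.** **The plan's own figures.** The documents state no number of tests, power or overall error rate. The only derived design figure is the completer count in Study Population, and it reproduces: 2 × (5 + 20 + 20) = 90 enrolled, and 90 × (1 − 0.20) = 72. It does not bear on multiplicity.

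**Step 1: on-drug compartment-by-time cells, from the visit sections.**

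| Visit | Samples | Cells |
|---|---|---|
| Phase II, visit 2 (4–6 h) | blood, urine, penile, urethral | 4 |
| Phase II, visit 3 (24 h) | those four, rectal secretions, rectal biopsies | 6 |
| Phase III, visit 3 (days 3–5) | blood, urine, penile, urethral | 4 |
| Phase III, visit 4 (day 10) | those four, rectal secretions, rectal biopsies | 6 |

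Total: 4 + 6 + 4 + 6 = 20. For the first row, for example, the protocol says "Four to six hours after the drug is taken, a urine sample, 4 tablespoons of blood will be drawn from the participants arm", with penile and urethral swabs also taken.

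**Step 2: analytes common to both arms.** Truvada is a "combination pill that contains the medications tenofovir and emtricitabine". Genvoya is a "combination anti-HIV medication that contains the drugs tenofovir alafenamide, emtricitabine, elvitegravir, and cobicistat". Assumption: one tenofovir measure and one emtricitabine measure per sample can be compared across arms, giving 2 shared analytes. Between-arm contrasts: 20 × 2 = 40.

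**Step 3: expected false positives at 0.05 each.** With *m* true nulls the expected number is 0.05 × *m*, whether or not the tests are independent. The chance of at least one is 1 − 0.95^*m*, which does need independence.

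If every null is true:

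| Reading of the schedule | Contrasts | Expected false positives | Chance of ≥ 1 (independent) |
|---|---|---|---|
| Penile and urethral swabs pooled: (3+5+3+5) × 2 | 32 | 1.6 | 81% |
| Rectal secretions not assayed: (4+5+4+5) × 2 | 36 | 1.8 | 84% |
| As in Steps 1 and 2 | 40 | 2.0 | 87% |
| Blood assayed as two matrices: (5+7+5+7) × 2 | 48 | 2.4 | 91% |

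If only some of the 40 nulls are true: 30 give 0.05 × 30 = 1.5, 20 give 1.0, and 10 give 0.5.

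Independence is unlikely, because several samples come from the same men at repeated visits and men may enter more than one phase. The expected counts are therefore the firmer figures.

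**Step 4: inflammatory markers.** The documents give no number of markers. A panel of *k* markers, each tested once at 0.05 with no true effects, adds 0.05 × *k*: 0.5 for 10 markers and 1.0 for 20. Both panel sizes are illustrations only.

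**Step 5: the tests the SAP does specify.** Within arms, the ceiling is 20 cells × (2 + 4) components = 120 tests. Multiplying 120 by 0.05 would mislead, because pre-drug levels should be near zero and most of those nulls are false.

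**The case against.** A reader might infer that the SAP applies 0.05 to every compartment, time, drug and inflammatory marker. The text does not support that. The threshold follows directly on a paired drug-level test, and the between-arm and inflammatory comparisons appear only in the protocol, without a threshold. The 40 contrasts are thus ones the SAP does not plan. For the tests it does plan, false positives should be few.

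A reader might also take about 2 false positives as a forecast. It is a ceiling for that count and needs all 40 nulls to be true. The protocol gives reason for doubt: the arms carry different tenofovir forms, and the Abstract calls tissue penetration of the newer agents unclear. If all 20 tenofovir contrasts truly differ, the expected number is 1.0.

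Finally, the documents make no confirmatory claim. They give no power statement, and several visit sections describe the samples as serving assay development at CDC. An exploratory study need not control an overall error rate.

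The first two objections stand, and they limit the size of the point. The third stands only in part. An exploratory study is entitled to skip adjustment, but neither document calls the analysis exploratory, and the SAP keeps a significance label. That the promised comparisons have no threshold of their own leaves them less constrained. It is fair to add that the missing between-arm test is the more basic gap, and that multiplicity follows from it.

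**Conclusion.** The point holds in a limited form. Neither document names a primary comparison or any multiplicity control. The SAP's single unadjusted 0.05 rule is attached to paired tests that do not address the protocol's comparative goal.

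If the intended between-arm drug contrasts were each tested at 0.05, up to about 2 false positives would be expected across about 40 contrasts (1.6 to 2.4 across 32 to 48). This rests on three assumptions: two shared analytes, separate assays for each sample type, and no true difference in any cell. The last makes the figure an upper value for each count.

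This is a wording gap that should be closed before results are compared by arm. It does not show that any planned test is invalid.

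**What to change.** Before the between-arm analysis, amend the SAP as follows.

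- Name one primary between-arm comparison. A defined tenofovir measure in rectal tissue at Phase III visit 4 would fit the rationale in the Abstract, which centres on exposure at the rectal mucosa and tissue penetration. The sponsor should confirm analyte and time, and state which tenofovir measure is comparable between arms.
- Test it at two-sided 0.05 with a two-sample method such as the Wilcoxon rank-sum test. The signed-rank test now in the SAP is paired and cannot compare independent arms.
- Report all other drug-level and inflammatory contrasts as estimates with 95% confidence intervals, labelled exploratory. If p-values are given for the inflammatory panel, false discovery rate control (for example Benjamini-Hochberg) is an option.

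A single primary test holds the type I error for the main claim at 5%. Bonferroni over 40 contrasts would instead require 0.05 / 40 = 0.00125 for each. That is severe with 20 men per arm in each dosing phase, or about 20 × 0.80 = 16 if the expected 20% non-completion falls evenly.

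The cost is SAP wording only, with no change to visits or samples. The downside is that secondary results can no longer be called significant one at a time.
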